1.0 Background

1.1 Myelofibrosis Unmet Clinical Needs

Myelofibrosis (MF) is a clonal myeloproliferative neoplasm (along with ET, PV, and CML) that can arise de novo, as primary myelofibrosis, or following essential thrombocythosis or polycythemia vera. Median age at diagnosis is 67 years old. Myelofibrosis is characterized by clonal stem cell proliferation, inefficient hematopoiesis, bone marrow fibrosis, and increased marrow vascularity. Bone marrow fibrosis and cytokine overexpression contribute to the cytopenias, extramedullary hematopoiesis (resulting in hepatosplenomegaly), and constitutional symptoms that are hallmarks of the disease. These associated symptoms can have considerable adverse effects on quality of life. Myelofibrosis is a heterogeneous disease that can follow an indolent course lasting years or a rapidly progressive course with attenuated survival. The Dynamic International Prognostic Scoring System- plus (DIPSS Plus) is a risk stratification system used to predict survival in primary MF. Early primary MF is defined as low or intermediate-1 risk and can be distinguished from advanced stages of the disease by evidence of residual hematopoiesis and grade 1 or 2 fibrosis on bone marrow biopsy.

Myelofibrosis is associated with a high morbidity and mortality resulting from marrow failure, massive splenomegaly, and leukemic transformation. Current drug therapies are not curative and have minimal impact on the natural history of the disease. Allogeneic stem cell transplant is the only known therapy with curative potential, however, advanced age at diagnosis and poor performance status prevent most patients from being transplant eligible.

1.2 Current available treatment

Current available treatments for primary MF target both the abnormal clonal stem cell proliferation and the pathologic bone marrow fibrosis. Unfortunately, bone marrow changes become irreversible in advanced stages of the disease, when patients become symptomatic and warrant treatment. Hydroxyurea has historically been shown to decrease hepatosplenomegaly, improve leukocytosis or thrombocytosis, and decrease constitutional symptoms in MF, however, it can cause cytopenias, is potentially leukemogenic, and effectiveness seems related to JAK2V617F mutation presence.

Recombinant interferon has shown efficacy in other myeloproliferative neoplasms (ET, PV) but dosing schedules were inconvenient and side effects limited use. Interferon α has induced cytogenetic and hematologic remissions in CML (another MPN) with evidence of reduction of marrow fibroblasts and bone marrow progenitor cells in vivo suggesting it may be effective in primary MF. (Gilbert HS. Cancer. 1998). Pegylated IFN α -2a has demonstrated efficacy, better tolerability, and a more reasonable dosing schedule. Hematologic responses are durable, and there has been no proven association with transformation to leukemia. A single institution study at Mayo Clinic showed rIFN α -2b monotherapy resulted in both hematologic and molecular responses in MF (Gowin Haematologica. 2012) A prospective single institution study of recombinant IFN α in 18 early MF patients (Silver Blood. 2011) showed an 80% rate of clinical benefit or stability with acceptable toxicities. JAK2 inhibitors have been approved for use in patients with intermediate or high risk MF and effectively reduce spleen size, improve constitutional symptoms, anemia, and quality of life. These medications appear best suited for patients with debilitating constitutional symptoms or severe symptomatic splenomegaly as opposed to patients with early stage myelofibrosis. Pegylated IFN α -2b has been studied in the treatment of hepatitis.

1.3

P1101

The study drug P1101 is a long acting pegylated interferon alpha-2b that has not yet been studied in MF. Preclinical safety data supports safe use of P1101 in humans. Clinical effects are expected to be similar to those of other approved Peg-IFN α products. Three clinical studies have looked at safety, efficacy, and maximum tolerated dose including one study in polycythemia vera patients. In this study, the MTD was found to be 540 μ g subcutaneously every two weeks. Among 34 evaluable patients, overall hematological response rate was 90% with complete response rates of 46% after one year of treatment. Sixteen serious adverse events have been reported. The incidence of treatment related emergent adverse events with P1101 was no higher than with Pegasys \circledR . Adverse events were mostly mild to moderate in severity and resolved spontaneously. Injection site erythema was the most common adverse event and headache was second.

Other reported adverse events included myalgia, decreased neutrophil count, back pain, increased body temperature, decreased white blood cell count, arthralgia, chills, fatigue, eye pain, feeling cold, nausea, transaminitis, somnolence, upper respiratory tract infection, feeling hot, decreased appetite, and pyrexia.

1.4

Rational

Patients with primary MF have a shortened life span and can have a significantly compromised quality of life as a result of progressive disease. Disease treatment earlier may delay progression of disease, prolong overall survival, and improve quality of life. We propose an open label nonrandomized pilot study of P1101 in patients with MF with the hypothesis that P1101 might have an impact in either early MF or in those with MF who are not eligible or failed ruxolitinib.

2.0 Goals

2.1 Primary

2.11 The primary objective in this study will be to evaluate for clinical response (complete remission [CR], partial remission [PR], or clinical improvement [CI]) as defined by IWG-MRT criteria (Tefferi et al. Blood. 2013) in a cohort of intermediate-2/high risk MF patients. Response in a second cohort of early stage MF patients will also be described.

2.2 Secondary

2.21 To evaluate the adverse event profile of P1101 in patients with myelofibrosis by cohort (early vs intermediate-2/high risk)

2.22 To evaluate the tolerability of P1101 in patients with myelofibrosis by cohort (early vs intermediate-2/high risk)

2.3 Exploratory and Correlative Research

2.31 To evaluate quality of life (QOL) and patient-reported symptoms using the MPN-SAF with P1101 for patients with myelofibrosis. (Emanuel et al. J Clin Oncol. 2012) by cohort (early vs intermediate-2/high risk)

2.32 To evaluate the impact of P1101 on bone marrow and histological features of myelofibrosis including cytogenetics, blast percentage, fibrosis, and JAK2-V617F allele burden by cohort (early vs intermediate-2/high risk)

3.0 Patient Eligibility

Overall: The study will enroll patients into two parallel cohorts – cohort 1, corresponding to the “early MF” definition, and the cohort 2, representing a “typical” MF patient. Enrollment will occur simultaneously for both cohorts , until the planned sample size will be achieved.

3.1 Inclusion Criteria

3.10 Evaluable myelofibrosis by IWG-MRT criteria including one or more of the following:

- Spleen \geq 5cm below the left costal margin
- MPN-SAF TSS $>$ 10 at baseline
- Hemoglobin $<$ 10 g/dL

3.11 Age \geq 18 years.

3.12 Confirmed diagnosis of myelofibrosis (primary myelofibrosis or myelofibrosis secondary to essential thrombocythemia or polycythemia vera) by WHO diagnostic criteria (3 major and 2 minor criteria: Major criteria: megakaryocyte proliferation and atypia with either reticulin and/or collagen fibrosis, not meeting criteria for CML, PV, MDS, or other myeloid neoplasm, JAK2V617F or other clonal marker or no evidence of reactive marrow fibrosis. Minor criteria: leukoerythroblastosis, increased LDH, anemia, palpable splenomegaly).

3.13 For cohort 1: Early stage MF (low or intermediate 1 stage as defined by DIPSS, see Appendix VI) without currently available treatment options.

For cohort 2: intermediate-2 or high risk MF patients as defined by DIPSS (see Appendix VI) either not eligible for ruxolitinib or having failed under ruxolitinib

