4.0 Test Schedule

Cycle = 28 days

Parameter	Prior to Registration ≤14 days	Active Monitoring					
		Cycle 1 Day 1	Cycle 1 Days 8, 15, 22 ±2 days	Cycle 2 and Cycle 3 Day 15	Prior to Treatment Cycle 2 Day 1 and Beyond	Prior to Treatment Cycles 2, 3, 6, 9 & 12 and every 3 cycles thereafter Day 1 ±3 days	At Treatment Discontinuation ±7 days
Medical History	X						
Prior Diagnosis/Prior Treatment	X						
Height (pre-study only)	X						
Weight, ECOG PS	X					X	X
Physical Examination	X					X	X
Serum pregnancy test(HCG) ³	X						
Vital Signs	X	X ⁷				X	X
CBC with Differential and peripheral blood smear (Can be from home lab for interval monitoring)	X		X ⁷	X ⁷	X ²		X
Chemistries (Sodium, potassium, creatinine, chloride, SGOT (AST), SGPT (ALT), Alkaline Phosphatase, Total bilirubin, glucose)	X		X ⁷	X ⁷	X ²		X
JAK2, BCR-ABL, CALR, & MPL	X ⁶					X ⁶	
Treatment Evaluation (see Section 11)						X	X
EKG	X						
Transfusion Assessment	X				X ⁵	X	X
Symptom Assessment Package (Patient Questionnaire Booklet)	X					X ¹	X

Parameter	Prior to Registration	Active Monitoring					
	≤ 14 days	Cycle 1 Day 1	Cycle 1 Days 8, 15, 22 ± 2 days	Cycle 2 and Cycle 3 Day 15	Prior to Treatment Cycle 2 Day 1 and Beyond	Prior to Treatment Cycles 2, 3, 6, 9 & 12 and every 3 cycles thereafter Day 1 ± 3 days	At Treatment Discon- tinuation ± 7 days
Clinical measurement of spleen and liver by physical exam	X					X	X
Research Blood Samples		X ⁷			X ^{7,8}		
Adverse Event monitoring	X	X ⁷	X ⁷		X ^{5,7}	X	X
Bone marrow biopsy and aspirate including cytogenetics ⁴	X					X	

Footnotes:

1. To be completed prior to treatment on Day 1. Patient questionnaire booklet must be used; copies are not acceptable for this submission.
2. To be completed on Day 1 of Cycles 4, 5, 7, 8, 10 and 11 at local MD office and faxed to study team
3. Pregnancy test must be completed ≤ 7 days prior to registration
4. ≤ 90 days prior to registration. Repeat at cycle 6 and 12 only.
5. Patients can be contacted by telephone for adverse event assessment when not seen in the clinic.
6. Must be completed at least 90 days prior to registration. Any positive results at baseline will be repeated again every three cycles (Cycle 3, 6, 9, etc).
7. Must be completed prior to treatment.
8. Research blood samples only collected on C1D1, C2D1, and C3D1 prior to treatment.

5.0 Grouping Factor:

Cohort: Cohort 1 (early stage MF) versus Cohort 2 (intermediate-2 or high risk MF)

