6.2 Correlative Research

A mandatory correlative research component is part of this study, the patient will be automatically registered onto this component (see Sections 3.19c and 14.0).

6.3 Documentation of IRB approval must be on file in the Registration Office before an investigator may register any patients.

In addition to submitting initial IRB approval documents, ongoing IRB approval documentation must be on file (no less than annually) at the Registration Office [REDACTED] [REDACTED] If the necessary documentation is not submitted in advance of attempting patient registration, the registration will not be accepted and the patient may not be enrolled in the protocol until the situation is resolved.

When the study has been permanently closed to patient enrollment, submission of annual IRB approvals to the Registration Office is no longer necessary.

6.4 Prior to accepting the registration, registration application will verify the following:

- IRB approval at the registering institution
- Patient eligibility
- Existence of a signed consent form

- Existence of a signed authorization for use and disclosure of protected health information

6.5 At the time of registration, the following will be recorded:

- Patient has/not given permission to store and use his/her sample(s) for future research of Myelofibrosis at Mayo.
- Patient has/not given permission to store and use his/her sample(s) for future research to learn, prevent, or treat other health problems.
- Patient has/not given permission for MCCC to give his/her sample(s) to researchers at other institutions.

6.6 Treatment cannot begin prior to registration and must begin \leq 14 days after registration.

6.7 Pretreatment tests/procedures (see Section 4.0) must be completed within the guidelines specified on the test schedule.

6.8 All required baseline symptoms (see Section 10.51) must be documented and graded.

6.9 Treatment on this protocol must commence at Mayo Clinic Arizona under the supervision of a hematologist or healthcare professional.

6.9a Study drug is available on site.

6.9b Patient questionnaire booklet is available on site; copies are not acceptable for this submission.

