Symptoms are evaluated by the Myeloproliferative Neoplasm Symptom Assessment Form total symptom score (MPN-SAF TSS).¹⁷ The MPN-SAF TSS is assessed by the patients themselves and includes fatigue, concentration, early satiety, inactivity, night sweats, itching, bone pain, abdominal discomfort, weight loss, and fevers. Scoring is from 0 (absent/as good as it can be) to 10 (worst imaginable/as bad as it can be) for each item. The MPN-SAF TSS is the summation of all the individual scores (0-to-100 scale). Symptoms response requires $\geq 50\%$ reduction in the MPN-SAF TSS.

Optional, Progressive disease assignment for splenomegaly requires confirmation my MRI or CT showing a $\geq 25\%$ increase in spleen volume from baseline. Baseline values for both physical examination and imaging studies refer to pre-treatment baseline and not to post-treatment measurements.

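### The only pre-dose symptom score is the screening one; for patients who enter on symptoms alone it is both qualifier and response baseline, which modestly inflates symptom responses

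*Combined protocol and SAP*

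**What the plan says.** Section 3.10 requires "Evaluable myelofibrosis by IWG-MRT criteria including one or more of the following": spleen at least 5 cm, hemoglobin below 10 g/dL, or "MPN-SAF TSS $>$ 10 at baseline". Any one is enough.

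In Section 4.0 the row "Symptom Assessment Package (Patient Questionnaire Booklet" is marked in the screening column ("Prior to Registration ≤14 days"), then before Cycles 2, 3, 6, 9, 12 and every third cycle after, and at discontinuation. The Cycle 1 Day 1 cell is blank. Footnote 1 ("To be completed prior to treatment on Day 1") is attached only to the column that begins with Cycle 2.

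Section 6.6 says: "Treatment cannot begin prior to registration and must begin \leq 14 days after registration".

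Section 11 says: "Symptoms response requires $\geq 50\%$ reduction in the MPN-SAF TSS". It does not name the reading that serves as baseline, and it sets no minimum baseline score, duration or confirmation visit for this component. Under Table 11.1 a symptom response can by itself give clinical improvement (CI). Section 16.11 counts CI as success, taking the best response over all cycles. Only cohort 2 is formally tested (Section 16.1).

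**The concern.** For a patient whose spleen is under 5 cm and whose hemoglobin is at least 10 g/dL, the screening total symptom score (TSS) decides entry and is then the denominator of the response. A score observed above a cut-off carries, on average, some upward error that later readings do not share. Part of any later fall is therefore regression to the mean. The direction favours efficacy, there is no control arm to absorb it, and the result feeds the primary endpoint through CI.

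The age of the score is a separate, lesser weakness: the baseline may not describe the patient at the start of treatment.

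**Working it through.** **1. Age of the baseline.** Up to 14 days before registration (Section 4.0) plus up to 14 days from registration to first dose (Section 6.6): 14 + 14 = 28 days at most.

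**2. Who is selected on TSS.** In Appendix VI, hemoglobin below 10 g/dL scores 2 and each of the other four factors scores 1. Without anemia the maximum is 4 points. High risk needs 5 or 6, so every high-risk patient has hemoglobin below 10 and qualifies whatever the TSS. An intermediate-2 patient (3 or 4 points) without anemia needs at least three of the other four factors. In cohort 2, selection on TSS therefore acts only on non-anemic intermediate-2 patients with a spleen under 5 cm. Their share is not given.

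**3. Size among those selected.** The documents give no mean, spread or repeatability for the TSS, so these are assumptions. The model has no drug effect: a gamma-distributed true score plus independent normal visit error, clipped to 0-100, with entry if the screening score exceeds 10. With total SD σ and repeatability r, the true-score SD is σ√r and the error SD is σ√(1−r). A response is a later score at or below half the baseline. Five visits match the booklets before Cycles 2, 3, 6, 9 and 12.

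Central case: mean 20, σ = 12, r = 0.8. Error SD = 12 × √0.2 = 5.4.

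| Patients | Visits | Screening baseline | Day 1 baseline | Difference (points) |
|---|---|---|---|---|
| Screening TSS > 10 | one | 8.8% | 6.6% | 2.2 |
| Screening TSS > 10 | best of five | 27.0% | 22.7% | 4.3 |
| Not selected on TSS | best of five | 29.8% | 29.8% | 0 |

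In the selected patients the mean score falls from 23.7 at screening to 22.6 at an independent Day 1 reading, about 1 point on the 0-100 scale.

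Over mean 15-25, SD 12-15 and repeatability 0.7-0.9, the best-of-five difference runs from 1.3 points (mean 25, SD 12, r = 0.9) to 10.9 points (mean 15, SD 15, r = 0.7). A wider grid (mean 12-30, true-score SD 10-18, same repeatability) stretches it to about 0-20 points. The high end belongs to populations with typical scores close to the cut-off.

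**4. Dilution.** Overall excess = share entering on TSS alone × excess among them. With an assumed share of one quarter, the central case gives 0.25 × 4.3 = 1.1 points.

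**5. What that means for the decision rule.** The chance of declaring the regimen worth further study is P(X₁ ≥ 4 of 12) + Σ P(X₁ = x) × P(X₂ ≥ 7 − x of 23), summed over x = 1 to 3. At true rates of 0.10 and 0.30 this gives 0.067 and 0.931, matching the 0.07 and 0.93 in Section 16.24. Adding 1 point to the null (0.11) gives 0.098 if Stage 2 is run. For Stage 1 alone, the only part now planned, the chance of 4 or more of 12 moves from 0.026 to 0.035. This assumes the excess adds to the 10% null; Section 16.21 does not say whether the 10% already allows for it.

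**The case against.** The strongest counter-argument is that the baseline is not the main source of chance responses. In the central case, moving from one visit to the best of five raises the rate from about 9% to 27%. Requiring two consecutive visits would bring it to about 7% with the screening baseline untouched, whereas a Day 1 baseline leaves about 23%. That is correct. The baseline change removes one bias of known direction and does not make the symptom component robust.

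The simulated figures also count symptom responses, not primary successes. CI further requires no progression, no worsening of cytopenias and minimum counts, none of which is modelled. The effect on the success rate would be somewhat smaller.

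Four stronger readings are tempting and are not supported:

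- **That the bias affects the whole trial.** It needs selection on TSS, and Section 3.10 offers two other routes. Where TSS did not decide entry, changing the baseline alters nothing on average.
- **That a 28-day-old score causes the inflation.** Selection causes it. Age adds variation, and untreated worsening would push the other way. The 28 days is also a maximum.
- **That every 2 points of excess doubles the false-positive chance.** Exact values at 0.10, 0.12 and 0.14 are 0.067, 0.135 and 0.228, so only the first step doubles. They assume Stage 2 is run, and they refer to points on the overall success rate, not points among patients selected on TSS.
- **That symptom response should also be restricted to patients with Day 1 TSS above 10.** That would again select on the reading used as denominator, and it adds a threshold absent from the response table the protocol adopts.

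Finally, footnote 1 might be read as requiring a Cycle 1 Day 1 booklet. It is not attached to that column, and the score used for entry must in any case exist before registration.

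**Conclusion.** The point holds in a limited form and is a cheap improvement, not a flaw that undermines the design. The documents establish that the screening TSS is the only scheduled pre-dose score, that it can be the sole qualifier, and that an unconfirmed halving of it can make a primary success.

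The direction is upward for patients entering on TSS alone. The size, about 1 to 11 points over five visits among them, rests wholly on assumed distributions and on visit errors being independent. If screening and Day 1 fall close together and their errors are correlated, a Day 1 baseline would remove only part of it. The trial-level effect is scaled down by a share the documents do not give. Cohort 1 is exposed to the same mechanism, but its results are descriptive only.

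**What to change.** In the Section 4.0 schedule, add the questionnaire booklet on Cycle 1 Day 1, completed before the first dose. In Section 11, define that score as the baseline for symptom response. State in Section 3.10 that the screening TSS serves eligibility only.

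Cost: one extra questionnaire at a visit where pre-treatment vital signs and research blood are already scheduled, and a slightly lower symptom-response count. Eligibility and the decision rule stay as they are.

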3.14 No prior treatment for myelofibrosis (for Cohort 1 only)

3.15 ECOG Performance Status (PS) 0, 1 or 2 (Appendix I).

3.16 The following laboratory values obtained \leq 14 days prior to registration.

- Platelet count \geq 100,000/mm³
- Absolute Neutrophil Count (ANC) \geq 1000/mm³
- Aspartate transaminase (AST) \leq 2.5 x ULN
- Alanine aminotransferase (ALT) \leq 2.5 x ULN
- Calculated creatinine clearance must be \geq 50 ml/min using the Cockcroft-Gault formula below:

Cockcroft-Gault Equation:

$$\text{Creatinine clearance for males} = \frac{(140 - \text{age})(\text{weight in kg})}{(72)(\text{serum creatinine in mg/dL})}$$

$$\text{Creatinine clearance for females} = \frac{(140 - \text{age})(\text{weight in kg})(0.85)}{(72)(\text{serum creatinine in mg/dL})}$$

- 3.17 Negative pregnancy test done \leq 7 days prior to registration, for women of childbearing potential only.
- 3.18 Ability to complete questionnaire(s) by themselves or with assistance.
- 3.19a Provide informed written consent.
- 3.19b Willing to return to enrolling institution for follow-up per section 4.0
- 3.19c Willing to provide blood samples for correlative research purposes (see Sections 6.2 and 14.0)

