8.0 Dosage Modification Based on Adverse Events

Treatment modifications are based on adverse events. All adverse events should be graded according to the CTEP Common Terminology Criteria for Adverse Events (CTCAE v4.0). Dose modification recommendations listed below are general guidelines, and appropriate dose adjustments for patient safety should be done as deemed necessary by the treating physician or his representative.

ALERT: *ADR reporting may be required for some adverse events (See Section 10)*

Dose Modifications for P1101 (Based on Adverse Events in Tables 8.2)

Starting Dose	Dose level -1	Dose level -2	Dose level -3	Dose level -4	Dose level -5	Dose level -6	Dose level -7
100 micrograms (mcg)	50 micrograms (mcg) Days 1 and 15	50 micrograms (mcg) Day 1 only	Discontinue				
150 micrograms (mcg)	100 micrograms (mcg)	50 micrograms (mcg) Days 1 and 15	50 micrograms (mcg) Day 1 only	Discontinue			
200 micrograms (mcg)	150 micrograms (mcg)	100 micrograms (mcg)	50 micrograms (mcg) Days 1 and 15	50 micrograms (mcg) Day 1 only	Discontinue		
250 micrograms (mcg)	200 micrograms (mcg)	150 micrograms (mcg)	100 micrograms (mcg)	50 micrograms (mcg) Days 1 and 15	50 micrograms (mcg) Day 1 only	Discontinue	
300 micrograms (mcg)	250 micrograms (mcg)	200 micrograms (mcg)	150 micrograms (mcg)	100 micrograms (mcg)	50 micrograms (mcg) Days 1 and 15	50 micrograms (mcg) Day 1 only	Discontinue

Table 8.2: Dose modification guidelines for P1101 related adverse events (with an attribution of possible, probable or definite)

→ → Use the NCI Common Terminology Criteria for Adverse Events (CTCAE) version 4.0* unless otherwise specified ← ←

CTCAE System/Organ/Class (SOC)	ADVERSE EVENT	AGENT	ACTION**
BASED ON INTERVAL ADVERSE EVENT PRIOR TO DAY 15 EACH CYCLE			
Investigations	Grade 3 Platelet count decreased	P1101	Omit Day 15 treatment until platelet count resolves to grade 2 or less. Treatment may be restarted at the next lower dose level
	Grade 4 Neutrophil count decreased	P1101	Omit Day 15 treatment until neutrophil count resolves to grade 2 or less. Treatment may be restarted at the next lower dose level
	Grade 3 Alanine aminotransferase (ALT) increased	P1101	Omit Day 15 treatment until ALT resolves to grade 2 or less. Treatment may be restarted at the next lower dose level
	Grade 3 Aspartate aminotransferase (AST) increased	P1101	Omit Day 15 treatment until AST resolves to grade 2 or less. Treatment may be restarted at the next lower dose level

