Non Hematologic	All other Non-Hematologic Toxicities Grade ≥ 3 (With the exception of nausea, vomiting or diarrhea controlled with appropriate medications.)	P1101	Omit Day 15 treatment and re-check weekly, when returns to \leq grade 2 resume treatment at next lower dose level.
AT TIME OF RETREATMENT ON DAY 1 OF EACH CYCLE			
Investigations	Grade 3 Platelet count decreased	P1101	Hold treatment until platelet count resolves to grade 2 or less, checking labs weekly. Treatment may be restarted at the next lower dose level. Contact study chair if treatment is held beyond 28 days.
	Grade 4 Neutrophil count decreased	P1101	Hold treatment until neutrophil count resolves to grade 2 or less, checking labs weekly. Treatment may be restarted at the next lower dose level. Contact study chair if treatment is held beyond 28 days.

CTCAE System/Organ/Class (SOC)	ADVERSE EVENT	AGENT	ACTION**
	Grade 3 Alanine aminotransferase (ALT) increased	P1101	Hold treatment until ALT resolves to grade 2 or less, checking labs weekly. Treatment may be restarted at the next lower dose level. Contact study chair if treatment is held beyond 28 days.
	Grade 3 Aspartate aminotransferase (AST) increased	P1101	Hold treatment until AST resolves to grade 2 or less, checking labs weekly. Treatment may be restarted at the next lower dose level. Contact study chair if treatment is held beyond 28 days.
Non Hematologic	All other Non-Hematologic Toxicities Grade \geq 3 (With the exception of nausea, vomiting or diarrhea controlled with appropriate medications.)	P1101	Hold treatment and re-check weekly, when returns to \leq grade 2 resume treatment at next lower dose level.

* Located at [REDACTED]

** Use the following to describe actions in the Action column:

- Omit = The current dose(s) for the specified drug(s) during a cycle is skipped. The patient does not make up the omitted dose(s) at a later time
- Hold/Delay = The current dose(s) of all drugs during a cycle is delayed. The patient does make up the delayed dose(s) when the patient meets the protocol criteria to restart drugs.
- Discontinue = The specified drug(s) are totally stopped.

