10.5 Other Required Reporting

10.51 Adverse events to be graded at each evaluation and pretreatment symptoms/conditions to be evaluated at baseline per the CTCAE v4.0 grading unless otherwise stated in the table below:

System/Organ/Class (SOC)	Adverse event/Symptoms	Baseline	Each evaluation
Investigations	White blood cell decreased	X	X
	Neutrophil count decreased	X	X
	Platelet count decreased	X	X
Gastrointestinal Disorders	Diarrhea		X
	# of stools	X	
	Nausea	X	X
	Vomiting	X	X

10.52 Submit via appropriate MCCC Case Report Forms (i.e., paper or electronic, as applicable) the following AEs experienced by a patient and not specified in Section 10.51

10.521 Grade 2 AEs deemed *possibly, probably, or definitely* related to the study treatment or procedure.

10.522 Grade 3 and 4 AEs regardless of attribution to the study treatment or procedure.

10.523 Grade 5 AEs (Deaths)

10.5231 Any death within 30 days of the patient's last study treatment or procedure regardless of attribution to the study treatment or procedure.

10.5232 Any death more than 30 days after the patient's last study treatment or procedure that is felt to be at least possibly treatment related must also be submitted as a Grade 5 AE, with a CTCAE type and attribution assigned.

10.53 Refer to the instructions in the Forms Packet (or electronic data entry screens, as applicable) regarding the submission of late occurring AEs following completion of the Active Monitoring Phase (i.e., compliance with Test Schedule in Section 4.0).

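### The first dose can rest on blood counts and chemistry up to 28 days old (pregnancy test up to 21), because no pre-dose laboratory check is scheduled on Cycle 1 Day 1

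*Combined protocol and SAP*

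**What the plan says.** Three clauses set the timing.

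- Protocol 3.16 covers platelets, ANC, AST, ALT and creatinine clearance: "The following laboratory values obtained \leq 14 days prior to registration".
- Protocol 3.17, repeated in footnote 3 of 4.0: "Negative pregnancy test done \leq 7 days prior to registration, for women of childbearing potential only".
- Protocol 6.6: "Treatment cannot begin prior to registration and must begin \leq 14 days after registration".

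In the 4.0 schedule, the Cycle 1 Day 1 column is marked for vital signs, adverse event monitoring and research blood. Each carries footnote 7, "Must be completed prior to treatment". The CBC, chemistry and hCG cells in that column are empty. CBC and chemistry next appear on Cycle 1 Days 8, 15 and 22 (±2 days) and on Day 15 of Cycles 2 and 3, all with footnote 7. hCG does not appear again.

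Table 8.2 contains the graded hold rules. Its title limits it: "Dose modification guidelines for P1101 related adverse events (with an attribution of possible, probable or definite". Its Day 1 block is headed "AT TIME OF RETREATMENT ON DAY 1 OF EACH CYCLE".

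**The concern.** All the entry laboratory values are tied to registration, and none is tied to dosing. Between registration and the first injection the plan orders no blood count, liver test or pregnancy test, although it orders CBC and chemistry before the second injection on Day 15.

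These are the measures that the drug and its class are expected to move. Sections 15.17 and 15.193 list falls in neutrophils, white cells and platelets, and changes in liver function. A platelet count or ALT that would stop a later Day 1 dose need not be measured before the first one.

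There is a plausible route to a hidden fall in counts. Exclusion 3.21 bars chemotherapy only in the 2 weeks before registration. A Cohort 2 patient could have chemotherapy 15 days before registration and qualifying laboratory tests 14 days before, that is, 1 day after the chemotherapy. A later fall in counts would not have to be seen before dosing.

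Interpretation also suffers. Actions under Table 8.2 depend on attribution to P1101, and without a current pre-dose value it is harder to tell whether an abnormal Day 8 result is new.

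**Working it through.** The plan states no figure for the age of a result at first dose, so there is none to reproduce. The check adds the permitted windows and then asks whether any other clause closes the gap.

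**1. Maximum age at first dose**

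Age = days from test to registration + days from registration to dose.

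| Test | Before registration | After registration (6.6) | Maximum age | If dosed on day of registration |
|---|---|---|---|---|
| CBC, chemistry | 14 (3.16) | 14 | 28 days | at most 14 |
| Pregnancy test | 7 (3.17) | 14 | 21 days | at most 7 |

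The first scheduled on-treatment CBC and chemistry fall on Day 8 ± 2, so Day 6 to Day 10.

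**2. Does another clause require a test or a hold?**

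- *6.7* refers back to 4.0 and adds nothing.
- *Footnote 8* of 4.0: "Research blood samples only collected on C1D1, C2D1, and C3D1 prior to treatment". This is the only blood ordered on Cycle 1 Day 1. Under 14.1 it is serum for banking, so it cannot inform dosing.
- *Table 8.2* cannot apply, for two reasons. A first dose is not a retreatment, and a value obtained before any P1101 cannot be attributed to P1101. The Day 15 block comes after the first dose.
- *Section 8.0* describes the dose changes as guidelines and leaves adjustment for safety to the treating physician. This does apply to the first dose, but it orders no test and sets no threshold.
- *10.51*: "Adverse events to be graded at each evaluation and pretreatment symptoms/conditions to be evaluated at baseline". It lists white cells, neutrophils and platelets. Adverse event monitoring is marked before dosing on Cycle 1 Day 1. If that day counts as an evaluation, grading those three items implies a current count. The text is ambiguous, orders no draw, and does not list AST, ALT or creatinine.

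So the gap is clear for AST, ALT, creatinine and hCG, and depends on the reading of 10.51 for blood counts.

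**3. How many repeat tests would a 14-day limit cause?**

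This needs an assumption, because actual intervals are not given. Let a be the age of the test at registration (0 to 14 days) and b the days from registration to dose (0 to a cap), with every whole day equally likely. Count the pairs with a + b > 14. The maximum is 19 patients (16.22).

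| Cap on b | Pairs over 14 days | Share | Of 19 patients |
|---|---|---|---|
| 0 | 0/15 | 0% | 0 |
| 3 | 6/60 | 10% | 1.9 |
| 7 | 28/120 | 23% | 4.4 |
| 14 | 105/225 | 47% | 8.9 |

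This range, about 0 to 9 patients, measures the workload of the fix. It does not count patients at risk. The documents give nothing from which to estimate how often a patient who met 3.16 would worsen to a hold-level grade before dosing.

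**4. Size of the exposure**

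The starting dose relative to the MTD that 1.3 reports for polycythemia vera is 100/540 = 0.185, or about 19%.

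**The case against.** Anchoring tests at registration and capping the start window is an accepted design, and the cap is 14 days. At most one 100 mcg dose precedes the Day 8 tests, and CBC and chemistry are required again before the Day 15 dose. Treatment starts on site under a hematologist or healthcare professional (6.9), who has discretion under Section 8.0. In Cohort 2, 16.211 pauses recruitment after 3 patients for a safety review. A patient who passed 3.16 would have to worsen considerably, untreated by P1101, before a Table 8.2 grade was reached. The pregnancy part concerns few patients: Section 1.1 gives a median age at diagnosis of 67, and 3.28 excludes people unwilling to use contraception.

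All of this stands, and it keeps the point small. It does not close the gap, because supervision and discretion cannot act on a value that nobody has to measure.

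A reader might go further in three ways that the documents do not support.

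- *Patients dosed on old results are ineligible.* Under 13.4 eligibility is judged at the time of registration, so a valid registration stays valid.
- *Nothing at all governs the first dose.* Section 8.0 gives discretion, and 10.51 can be read as calling for current counts.
- *Every Day 1 hold in Table 8.2 should be copied to the first dose.* That would include any other non-hematologic condition of Grade 3 or higher. Entry has no general bar on such conditions: 3.15 admits ECOG 2, and symptom burden is itself a qualifying feature under 3.10. A validly registered patient with Grade 3 fatigue from myelofibrosis could be held, fail to improve within 14 days, be cancelled, and drop out of the evaluable set in 16.11. That would be an unstated eligibility criterion acting against the sickest patients.

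**Conclusion.** The point holds as a missing pre-dose check. As written, the first dose may be given on CBC and chemistry up to 28 days old and a pregnancy test up to 21 days old, with no graded hold rule in force. Those ages are worst cases that follow directly from 3.16, 3.17 and 6.6; typical ages are unknown. The gap is firm for AST, ALT, creatinine and hCG, and rests on an ambiguous reading of 10.51 for white cells, neutrophils and platelets. The pregnancy part is secondary. The safety risk is modest and cannot be quantified from the documents. Best overall response, the two-stage rule and its error rates are unaffected. This is a cheap improvement.

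**What to change.** Keep registration as the anchor for eligibility, and make two changes.

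1. In 4.0, add a Cycle 1 Day 1 pre-dose mark (footnote 7) for CBC and chemistry when the screening values are more than 14 days old, and for hCG in women of childbearing potential when the test is more than 7 days old. Maximum ages at first dose then fall from 28 to 14 days and from 21 to 7 days.
2. In Section 8, state that the first dose is held for a platelet decrease of Grade 3 or higher, a Grade 4 neutrophil decrease, or an ALT or AST increase of Grade 3 or higher, regardless of attribution, until Grade 2 or less. The patient then starts at dose level 0, since there is no earlier dose to reduce. A positive pregnancy test means no dosing. Do not extend this hold to other non-hematologic conditions.

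A patient who cannot start within the 14 days of 6.6 is a cancel under 13.6.

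The cost is an amendment to one table and a short addition to Section 8. Some patients (about 0 to 9 of 19 under the assumption above) need routine tubes at the existing Cycle 1 Day 1 draw and a short wait for results. No new visit is needed. An occasional delay or cancel is possible, and in Cohort 2 a cancel could use up the single spare patient that 16.22 allows for Stage 1.
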